2 RATIONALE

As discussed, the provision of CAH at the end-of-life is one of the most contentious issues in medicine. The “issue” is not new [18], and the debate primarily continues due to the lack of evidence for/against CAH [3,4]. Recently, the “issue” has received greater attention due to the widespread negative publicity about the Liverpool Care Pathway (LCP), and the subsequent Neuberger review of the LCP (which resulted in withdrawal of the LCP in the UK) [2].

The Neuberger review noted that “most of the submissions to the Review from relatives and carers that were critical of the LCP made reference to hydration and nutrition” [2]. Moreover, the Neuberger review comments that “if fluids are stopped without review over many days, death from dehydration will be inevitable, the lack of hydration having accelerated the dying process” [2]. It should be noted that the Neuberger review also highlighted concerns about the use of sedative drugs at the end-of-life (see above).

Data from recent national audits of end-of-life care in hospitals in the UK suggests that there has been an increase in the number of patients receiving CAH in the last days of life [19,20]. Thus, 29% patients were receiving CAH “at the time of the patient’s death” in 2013, whilst 43% patients were receiving CAH “in the last 24 hours before the patient’s death” in 2016 [20]. This major change in practice does not relate to any new evidence (or, indeed, any new guidance), and undoubtedly reflects the widespread negative publicity around the LCP, and specifically the negative publicity around withholding/withdrawing CAH at the end-of-life [2].

In terms of guidance, the NICE guideline on care of dying adults in the last days of life states that healthcare professionals should “discuss the risks and benefits of clinically assisted hydration with the dying person and those important to them” [21]. However, the NICE guideline highlights the lack of evidence on CAH (in order to do so): “clinically assisted hydration may relieve distressing symptoms or signs related to dehydration but may cause other problems”; “it is uncertain if giving clinically assisted hydration will prolong life or extend the dying process”; “it is uncertain if not giving clinically assisted hydration will hasten death” [21].

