3 OBJECTIVES AND OUTCOME MEASURES/ENDPOINTS

Our hypothesis is that CAH in the last days of life reduces the prevalence of delirium (and the requirement for sedative medication), as a result of preservation of renal function, and

prevention of build-up of drugs and toxins. Furthermore, CAH will prevent death due to dehydration occurring before death due to the underlying disease (or its complications).

The aim of this cluster randomised trial is to fully evaluate CAH in patients in the last days of life. The primary objective is to assess the effect of CAH on prevalence of delirium. The secondary objectives are to assess the: a) effect of CAH on prevalence of audible upper airway secretions ("death rattle"); b) effect of CAH on prevalence of pain and other symptoms (shortness of breath, nausea and vomiting); c) tolerability of CAH; d) effect of CAH on survival; e) health economic impact of CAH; and f) differences in response to CAH between participants with cancer and participants with non-malignant disease.

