7.6 Trial assessments

The trial lasts for 14 days (maximum). However, it is expected that the majority of participants will have died within this time period (of their primary disease).

Participants will be reviewed every four hours during the trial by the clinical team, and the following assessments completed (by the clinical team):

- ❖ Nu-DESC score (see above)
- ❖ m-RASS score (see above)
- ❖ Presence of audible upper airway secretions (“death rattle”)
- ❖ Presence of pain – patient reported
- ❖ Presence of shortness of breath – patient reported
- ❖ Presence of nausea and vomiting – patient reported (nausea and vomiting), or nurse assessment (vomiting)
- ❖ Presence of adverse effects of CAH (see above)

The clinical team will also record the participant's fluid intake (oral, CAH), and medications / other interventions provided to the participant (and the indications) during the trial.

Data on usage of CAH paraphernalia (e.g., cannulae, giving sets), and paraphernalia relating to other interventions will also be recorded (to support the health economic analysis).

Overall survival (from the time of randomisation) will be recorded. [Participants that survive >14 days will continue to be followed up in order to determine their date of death].

The clinical team will complete a trial-specific clinical observation document, which will be transcribed by the research team into the case report form (CRF). The research team will also use the participant's clinical notes and drug charts as source documents.

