9 PHARMACOVIGILANCE

9.1 Definitions

Term	Definition
Adverse Event (AE)	Any untoward medical occurrence in a participant to whom a medicinal product or intervention has been administered, including occurrences which are not necessarily caused by or related to that product.
Serious Adverse Event (SAE)	A serious adverse event is any untoward medical occurrence that: 
• results in death• is life-threatening• requires inpatient hospitalisation or prolongation of existing hospitalisation• results in persistent or significant disability/incapacity• consists of a congenital anomaly or birth defect Other 'important medical events' may also be considered serious if they jeopardise the participant or require an intervention to prevent one of the above consequences. NOTE: The term "life-threatening" in the definition of "serious" refers to an event in which the participant was at risk of death at the time of the event; it does not refer to an event which hypothetically might have caused death if it were more severe.

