9.2 Operational definitions for AEs and SAEs

As the trial is being undertaken in participants in the last days of life, progression of existing problems, and development of typical end-of-life problems (e.g., delirium, audible upper airway secretions) are not considered to be AEs / SAEs (and so are not reportable). Similarly, death related to the primary disease / complication of the primary disease is not considered an SAE, nor is inpatient hospitalisation or prolongation of existing hospitalisation, because all participants will already be in a hospital or hospice.

The development of localised swelling at the site of infusion, or the requirement to re-site the cannulae are not considered AEs (and so are not reportable). Other complications of the CAH (e.g., peripheral oedema, pulmonary oedema) will be considered as AEs / SAEs (and so are reportable). Death directly related to the CAH is considered an SAE.

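### Adverse-event reporting is defined by reference to CAH only, so AE/SAE tables can differ between arms because of the definition rather than because of true events

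*Protocol*

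**What the plan says.** Section 8 makes both approaches randomised interventions: standard intervention A (no CAH) and standard intervention B (CAH).

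Section 9.2 sets the operational reporting rules:
- On complications: "Other complications of the CAH (e.g., peripheral oedema, pulmonary oedema) will be considered as AEs / SAEs (and so are reportable").
- On deaths: "Death directly related to the CAH is considered an SAE", whereas "death related to the primary disease / complication of the primary disease is not considered an SAE".
- On exemptions, in either arm: "development of typical end-of-life problems (e.g., delirium, audible upper airway secretions) are not considered to be AEs / SAEs (and so are not reportable").

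The adverse-effect endpoint in 3.2, the four-hourly item in 7.6 and the corresponding row of Table 3 are all framed as adverse effects of CAH.

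Section 9.1 gives a general AE definition that is wider, "including occurrences which are not necessarily caused by or related to that product". Section 9.3 has all AEs recorded in the CRF and asks, for each SAE, whether it was related to the intervention.

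Section 3 hypothesises that "CAH will prevent death due to dehydration occurring before death due to the underlying disease" or its complications.

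**The concern.** If giving and not giving CAH are both trial interventions, harm from either is intervention-related harm. Section 9.2 names it for arm B only. Two consequences follow.

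First, the protocol's own hypothesis names a fatal harm of not giving CAH, but no event category, reporting trigger or cause-of-death attribution goes with it. A site could file such a death as a complication of the primary disease, which is exempt.

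Second, the same clinical finding can be reportable in one arm and exempt in the other, because what makes it reportable is its presumed cause. The trial is unblinded (7.4), so staff making that call know whether fluid is running.

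At stake is how the AE and SAE tables by arm can be read, both in the final report and wherever the DMEC relies on AE/SAE data. The delirium and survival comparisons are not at stake.

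**Working it through.** No figure in the protocol bears on this point, so the check sets the sections side by side.

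1. **Peripheral oedema.** Section 8.3 describes it as common at the end of life and usually unrelated to over-hydration. Section 9.2 lists it as a reportable complication of CAH. Section 9.2 also exempts typical end-of-life problems. In arm B, oedema meets the named reportable category. In arm A there is no CAH for it to complicate, and 8.3 gives the site grounds to call it typical and leave it unreported.

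2. **Death from dehydration.** Section 3 separates it from death due to the underlying disease or its complications. Section 9.2 exempts the latter and names only CAH-related death as an SAE. Death from dehydration is therefore neither named nor expressly exempted. The general definition in 9.1 could capture it, but each site has to decide.

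3. **Ascertainment.** Dehydration is formally judged at entry (6.2, criterion a; Appendix 5), and no repeat assessment is listed in 7.6 or Table 3. After entry it appears only if a site reports it as an AE or gives it as the reason for starting CAH (7.8).

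4. **Route to oversight.** Section 9.4 sends safety information to the DMEC and/or TSC according to the Trial Monitoring Plan. Section 10.6 plans no interim analysis, though the DMEC reviews data periodically and may ask for one.

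The form of the artefact can be written down. Suppose oedema has the same true probability *p* in both arms, every case in arm B is reported, and sites exempt a share *x* of the cases in arm A.
- Reported proportion in arm B: *p*
- Reported proportion in arm A: *p*(1 − *x*)
- Spurious difference: *p* − *p*(1 − *x*) = *px*
- Spurious ratio, A to B: *p*(1 − *x*)/*p* = 1 − *x*

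With 1600/2 = 800 participants per arm, the expected excess of reports in arm B is 800*px*. At *x* = 0 it is zero. At *x* = 1 it is 800*p*, and arm A reports nothing. The protocol gives neither *p* nor *x*, and nothing in 9.2 keeps *x* near zero.

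**The case against.** The strongest reply is that the main hypothesised harms of withholding fluid are already measured. Section 3 runs from preserved renal function to less delirium and less sedation. Delirium is the primary endpoint, and m-RASS, pain, breathlessness, nausea and vomiting are recorded four-hourly in both arms. All-cause survival is followed past day 14, so whether death comes sooner without CAH is tested. This stands. A reader might infer that the protocol looks only for harms of giving fluid, and the documents do not support that.

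Next, the definitions in 9.1 and 9.3 are not limited by arm. On the wording of section 3, a dehydration death is not a complication of the primary disease, so the 9.2 exemption does not strictly reach it. This also stands: the event is unaddressed, not declared non-reportable. But it leaves classification to individual sites, which is the weakness.

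Third, one secondary objective is the tolerability of CAH, and a CAH-specific endpoint suits it. That justifies the 3.2 endpoint as a description of arm B. It does not justify AE/SAE rules that depend on presumed cause in a two-arm comparison.

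Fourth, the content of DMEC reports is left to the Trial Monitoring Plan, and the 7.6 item is not expressly restricted to arm B. Both are fair. They make a distorted table possible rather than certain.

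A reader might also infer that dehydration must be frequent in arm A, from the entry criterion of oral intake below 1 L/day and the volumes in Table 4. At 60 kg the gap is more than 1.5 − 1 = 0.5 L/day, but at 40 kg it is only more than 1 − 1 = 0. Section 8.2 describes the 25 ml/kg/day basis as an upper limit for consideration in old or frail participants. Nothing in the protocol turns such a gap into a rate of clinical dehydration.

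**Conclusion.** The point holds for safety reporting. Reportable harm is defined by reference to CAH, a hypothesised harm of withholding has no named category, and at least one finding, peripheral oedema, can be classified differently by arm under the protocol's own text. Harms of withholding enter only through endpoints measured in both arms and all-cause survival, which cannot attribute a death to dehydration.

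The size cannot be stated. The spurious difference is *px*, and both quantities are unknown. The conclusion assumes that some arm A sites would use the 9.2 exemptions where arm B sites would report. The text permits this but does not require it. The primary analysis and the survival comparison are not affected. The change is worth making because it is cheap and because AE/SAE tables by arm cannot otherwise be read at face value.

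**What to change.** Reconcile sections 3, 8.3, 9.1 and 9.2 by making 9.2 arm-neutral:
- Apply one list of events in both arms (for example peripheral oedema, pulmonary oedema and clinical dehydration), recorded whatever the presumed cause. State that listed events are not covered by the exemption for typical end-of-life problems.
- Treat complications and deaths judged directly related to the allocated hydration approach, whether giving or not giving CAH, as AEs/SAEs in both arms. Use the causality field that 9.3 already provides, and tabulate the results by arm.

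The 3.2 endpoint can stay as the description of CAH tolerability.

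The cost is a change of wording, slightly more recording and no new tests. Attribution remains an unblinded judgement, so the listed events should be shown by arm irrespective of attribution as well as by attribution.

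A separate scheduled dehydration outcome is not part of this change. Appendix 5 reports no indicator of high accuracy, and staff who know whether fluid is running would be making the judgement.

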9.3 Recording and reporting of SAEs

All AEs will be recorded in the CRF, and SAEs must be reported to Surrey CTU, acting on behalf of the Sponsor, within 24 hours. AEs / SAEs recording starts from the time the participant consents to take part in the trial. AEs will continue to be recorded / reported until the end of the trial (i.e., ≤ 14 days).

The following information will be collected about SAEs (on a specific form): a) full details in medical terms and case description; b) event duration (start and end dates, if applicable); c) action taken d) outcome e) seriousness criteria f) causality (i.e., relatedness to intervention), in the opinion of the investigator; g) whether the event would be considered anticipated. AEs will be followed up until resolved or a final outcome has occurred.

9.4 Responsibilities

Principal Investigator (PI)

1. Checking for AEs.
2. Using medical judgement in assigning seriousness, causality and whether the event/reaction was anticipated.
3. Ensuring that all SAEs are recorded and reported to Surrey CTU within 24 hours of becoming aware of the event and provide further follow-up information as soon as available.

4. Make certain that SAEs are followed up with Surrey CTU if a record of receipt is not received within 2 working days of initial reporting.
5. Ensuring that all AEs are documented fully in the back of the CRF.

Chief Investigator (CI) / delegate

1. Clinical oversight of the safety of participants participating in the trial, including an ongoing review of the risk / benefit.
2. Using medical judgement in assigning the SAEs seriousness, causality and whether the event was anticipated where it has not been possible to obtain local medical assessment.
3. Review of specific SAEs in accordance with the trial risk assessment and protocol as detailed in the Trial Monitoring Plan.
4. Assigning Medical Dictionary for Regulatory Activities (MedDRA) or Body System coding to all SAEs.

Surrey Clinical Trials Unit, acting on behalf of the Sponsor

1. Central data collection and verification of AEs and SAEs onto a database, in accordance with the trial protocol.
2. Reporting safety information to the CI, delegate or independent clinical reviewer for the ongoing assessment of the risk / benefit according to the Trial Monitoring Plan.
3. Reporting safety information to the independent oversight committees identified for the trial DMEC and / or TSC) according to the Trial Monitoring Plan.

Trial Management Group (TMG)

The TMG will regularly review safety events and ensure onward reporting and notification to the Sponsor and oversight committees in accordance with their Terms of Reference.

9.5 Reporting urgent safety measures

If any urgent safety measures are taken, the CI / Sponsor shall immediately, and in any event no later than 3 days from the date the measures are taken, give written notice to the relevant Research Ethics Committee (REC) of the measures taken and the circumstances giving rise to those measures.

10 STATISTICS AND DATA ANALYSIS

10.1 Sample size calculation

The sample size is based on a “clinically meaningful” reduction in the proportion of participants developing delirium in the CAH intervention group (versus the non-CAH intervention group): a figure of 10% was deemed to be appropriate by the clinicians involved in the trial, and this figure was supported by clinical colleagues (i.e., palliative care doctors / nurses), and members of the local PPI group.

To demonstrate a reduction of 10% in the proportion of participants developing delirium (defined as having a score of > 0 on the Nu-DESC scale) would require 1038 evaluable participants with 90% power and at a significance level of 0.5. The calculation assumes the incidence of delirium in the non-CAH intervention group of 60% (as observed in the feasibility trial). To account for clustering in the responses of participants within centres of size 20, the sample size will be inflated by 1.475 using an estimate of the intra-cluster correlation of 0.025 (as observed in the feasibility trial). A further allowance of 5% for attrition suggests that 80 centres will be required (delivering 1600 participants).

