3.1 Primary endpoint/outcome

The primary endpoint is the proportion of participants that develop delirium at any point during the trial. The Nursing Delirium Screening Scale (Nu-DESC) will be used to identify participants with delirium: the Nu-DESC is a validated, five item screening tool for delirium (Table 1) [23], which is endorsed for use at the end of life [24], and which was utilised in a recent Australian, multicentre, phase 2, CRT of a multimodal intervention to prevent delirium in participants with advanced cancer [25]. The Nu-DESC will be completed as part of the regular four hourly assessment of participants, and also when a participant is administered either "as-required" or regular medication for delirium (unless the latter relates to the regular four hourly assessment of the participant). Each "feature" on the Nu-DESC is rated from 0-2 (where 0 = absent, and 2 = severe), and a total score of >1 is indicative of delirium (although a total score of > 0 has a higher sensitivity with a similar specificity) [26]. A cut-off of > 1 is more clinically relevant (for a trial involving patients in the last days of life), and a score of > 1 in domain 5 / psychomotor retardation is indicative of hypoactive delirium (vs. hyperactive delirium).

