3.2 Secondary endpoints/outcomes

The secondary endpoints are:

- ❖ Proportion of participants with Nu-DESC total score of > 0 at any point during the trial.
- ❖ Nu-DESC scores during trial (mean score during the trial; proportion time with score 0; proportion time with score > 0; proportion of time with score > 1).
- ❖ Time to first episode of Nu-DESC score > 1.
- ❖ Proportion of participants that receive as-required and/or regular medication specifically for delirium at any point during the trial (data derived from drug chart).

- ❖ Time to first dose of medication for delirium (as-required or regular – data derived from drug chart).
- ❖ Modified Richmond Agitation and Sedation Scale (m-RASS) scores during trial (mean score during the trial; proportion time with score 0; proportion time with score 0 to -2 – data derived from clinical observation document). The RASS is a validated measuring tool for severity of agitation and level of sedation, and the m-RASS has been modified for/validated in patients with advanced cancer (Table 2) [27].
- ❖ Proportion of participants with audible upper airway secretions at any point during the trial (“death rattle” – data derived from clinical observation document).
- ❖ Time to first episode of audible upper airway secretions.
- ❖ Proportion of participants that receive as-required and/or regular medication specifically for audible upper airway secretions at any point during the trial (data derived from drug chart).
- ❖ Time to first dose of medication for audible upper airway secretions (as-required or regular – data derived from drug chart).
- ❖ Proportion of participants that experience pain, shortness of breath, and nausea and vomiting (and require medication for these symptoms – data derived from clinical observation document and drug chart).
- ❖ Adverse effects of CAH, e.g., peripheral oedema, pulmonary oedema, cannula site inflammation, cannula site infection. (Data derived from clinical observation document)
- ❖ Overall survival (data derived from clinical observation document). Participants that survive >14 days will continue to be followed up in order to determine their date of death.
- ❖ Participant level costs (data derived from clinical observation document and drug chart) and cost effectiveness based on reductions in the likelihood of delirium.

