10.3.2 Primary outcome analysis

The primary analysis will use a multilevel regression approach, which recognises the hierarchical nature of the data, and participants nested within centres (clusters). A mixed effects logistic regression will be used to assess the difference in the odds of delirium (defined as a Nu-DESC score ≥ 2 at any point during the trial observation period) between intervention groups, using intervention group as a covariate and adjusting for home country (i.e., England, Wales, Scotland or Northern Ireland) and by type of unit (i.e., hospital or hospice), which were used as stratification variables in the randomisation, disease category (i.e., cancer, non-malignant disease), age (e.g., < 65 years, > 65 years), and sex (i.e., male, female). Centre will be included as a random effect, to allow for correlation in outcomes within clusters. A significance level of 5% will be used to judge significance for the primary outcome measure. The analysis will take into account different “times at risk” by adding an offset term of log (observed days to delirium) to the model, effectively adjusting the binomial denominator to reflect the number of “trials” in each participant.

A sensitivity analysis for the primary outcome will be undertaken per-protocol excluding those participants who did not comply with the protocol. Compliance with the CAH regimen will be defined as receiving $>75\%$ of the prescribed fluids.

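### Section 10.1 states 90% power for Nu-DESC > 0, a secondary endpoint, so the power for the primary endpoint (Nu-DESC > 1) is unsupported as labelled

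*Protocol*

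**What the plan says.** Four places in the Protocol bear on this.

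- **Section 10.1 (sample size).** Delirium is "defined as having a score of > 0 on the Nu-DESC scale) would require 1038 evaluable participants with 90% power". The control incidence is 60% and the ICC 0.025, both attributed to the feasibility trial, and the target is a reduction of 10%. The level is printed as "at a significance level of 0.5". Clustering is handled thus: "To account for clustering in the responses of participants within centres of size 20, the sample size will be inflated by 1.475". After 5% attrition the result is 80 centres and 1600 participants.
- **Section 3.1 (primary endpoint).** The primary threshold is a total score above 1, chosen over above 0 because "A cut-off of > 1 is more clinically relevant" for patients in the last days of life.
- **Section 3.2 (secondary endpoints).** The first item is "Proportion of participants with Nu-DESC total score of > 0 at any point during the trial".
- **Section 10.3.2 (primary analysis).** Delirium is "defined as a Nu-DESC score ≥ 2 at any point during the trial observation period", and "A significance level of 5% will be used to judge significance for the primary outcome measure".

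Nu-DESC totals are whole numbers (five items, each scored 0, 1 or 2), so above 1 and at least 2 are the same threshold. Sections 3.1 and 10.3.2 agree with each other, and section 10.1 is the one that differs. Section 10.3.3 also treats the cut-offs of 1 and 2 as separate outcomes.

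**The concern.** The power statement is the justification for enrolling 1600 dying patients, and it should refer to the endpoint on which the trial will be judged. As written it refers to another one. Everyone who scores above 1 also scores above 0, so the primary incidence cannot exceed the above-0 incidence. If 60% is the above-0 rate, 60% against 50% is not the scenario for the primary endpoint unless the two rates happen to coincide. The ICC may also differ between thresholds.

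The size of the target is affected too. Ten points is one sixth of 60%, but one quarter of 40% and one third of 30%. Section 10.1 reports that clinicians and the patient and public involvement group supported the 10% figure. It does not say that they were asked about it at a lower base rate.

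Two smaller matters sit in the same paragraph: the printed significance level, and a design effect that assumes every centre contributes exactly 20 participants.

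**Working it through.** **1. Reproducing the plan's figure.** Inputs from section 10.1: 60% against 50%, 90% power. Level from section 10.3.2: 5%, taken as two-sided. Pooled-variance formula for two proportions, no continuity correction:

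n per arm = [1.960 × √(2 × 0.55 × 0.45) + 1.2816 × √(0.60 × 0.40 + 0.50 × 0.50)]² / 0.10² = (1.379 + 0.897)² / 0.01 = 518.04, so 519 per arm and **1038** in total. This matches exactly.

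The same formula at other levels:

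| Level | Total |
|---|---|
| 0.05 two-sided | 1038 |
| 0.05 one-sided | 846 |
| 0.5 two-sided | 378 |
| 0.5 one-sided | 162 |

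Of these, only two-sided 0.05 gives the stated number.

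**2. Clustering and attrition.** Design effect = 1 + (20 − 1) × 0.025 = 1.475, as stated. 1038 × 1.475 = 1531.05, and 1531.05 / 0.95 gives 1612, or 81 centres of 20, against the stated 1600 and 80. The gap is trivial: 1600 × 0.95 = 1520 evaluable, 19 per centre, design effect 1 + 18 × 0.025 = 1.45, power 90.3% (89.8% if 1.475 is kept). On its own inputs the calculation is sound.

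**3. Power at the primary threshold.** The Protocol gives no rate for Nu-DESC > 1, so the control rates below are assumed. 1520 evaluable, 19 per centre, ICC 0.025, two-sided 0.05. Effective number per arm = 1520 / 1.45 / 2 = 524.1. Three readings of the effect:

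- the absolute 10 points;
- the planned odds ratio, (0.5/0.5) / (0.6/0.4) = 0.667;
- the planned relative reduction, 10/60 = one sixth.

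| Control rate at > 1 | Absolute 10 points | Odds ratio 0.667 | One-sixth relative |
|---|---|---|---|
| 60% | 90.3% | 90.3% | 90.3% |
| 55% | 90.0% | 90.6% | 84% |
| 50% | 90.3% | 90% | 77% |
| 40% | 92.5% | 88% | 61% |
| 30% | 96.3% | 82% | 44% |

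Worked cell, 40% against 30%: z = [0.10 × √524.1 − 1.960 × √(2 × 0.35 × 0.65)] / √(0.40 × 0.60 + 0.30 × 0.70) = (2.289 − 1.322) / 0.671 = 1.44, power 92.5%.

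**4. A different ICC.** At 60% against 50% with equal clusters, power is 95.1% at ICC 0.01, 84.9% at 0.04 and 81.3% at 0.05. These alternative ICCs are assumed.

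**5. Unequal centres.** Design effect = 1 + [(1 + CV²) × 19 − 1] × 0.025, where CV is the coefficient of variation of centre size, which is assumed. At CV 0.4 this is 1.526 and power is 88.8%; at CV 0.65 it is 1.651 and power is 86.3% (60% against 50%).

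**The case against.** The strongest reply is that nothing here shows the trial to be short of power, and that is right. A reader might infer from the mismatch that 90% is not the power of the primary endpoint. The Protocol does not support that, for two reasons.

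- The 60% and 0.025 may be the feasibility trial's figures for Nu-DESC > 1, with only the label in section 10.1 wrong. In that case 90% is the primary endpoint's power.
- If 60% is the above-0 rate, the stated target is still 10 points, and section 10.10 describes the reduction as absolute, although for the economic measure. On that scale, with the ICC unchanged, power does not fall materially below 90% at any lower control rate.

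The lower figures in the last two columns of the table replace the Protocol's target with a constant odds ratio or a constant relative reduction, and it states neither. They show what rests on confirming the target; they are not errors in the calculation.

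A reader might also take the printed 0.5 as evidence that the power is wrong. It is a misprint: section 10.3.2 says 5%, and 1038 follows from two-sided 0.05.

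Nor do unequal centres prove a loss. The Protocol gives no CV. Section 10.2 assumes that centres open quickly, and the 40 sites at 12 months in Table 5 are a progression threshold, not an opening schedule.

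What stands is the contradiction itself. Sections 3.1 and 10.3.2 cannot both be reconciled with section 10.1 as printed. A statistical analysis plan does not cure this, because the Protocol itself states the figure, and states it for the other threshold.

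**Conclusion.** The point holds in a limited form. Section 10.1 is wrong as written: it attaches the 90% power to a secondary endpoint, so the power for the primary endpoint is unsupported as labelled, but not shown to be lower. The arithmetic reproduces, and the defect is one of endpoint definition.

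The size depends on facts the Protocol does not give. With 10 absolute points and ICC 0.025, power stays at about 90% or more. With a one-sixth relative reduction and a 40% control rate, both assumed, it would be 61%. With a larger ICC, such as an assumed 0.04 at 60% against 50%, it would be about 85%.

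The misprinted level has no effect on any number. The equal-centre assumption costs perhaps 1.5 to 4 points under assumed CVs of 0.4 to 0.65. Both are secondary to the threshold contradiction.

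**What to change.** In section 10.1:

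1. Restate the calculation for Nu-DESC > 1, with the feasibility trial's control incidence and ICC at that threshold. If 60% and 0.025 already refer to > 1, correct the label instead.
2. Confirm that an absolute 10-point reduction is still the target at that base rate, and say in this section that it is absolute.
3. Give the resulting power at 80 sites and 1600 participants.
4. Correct the significance level to two-sided 0.05, to agree with section 10.3.2.
5. Optionally, note that 1.475 assumes equal centres of 20, and report power under a stated cluster-size CV.

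The cost is some rewording and one recalculation from the feasibility data on which the paragraph already draws. The stated power may change slightly. No extra participants or sites are needed.
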